### Eligibility Criteria Venous Leg Ulcer (VLU):

#### **Inclusion Criteria:**

- 1. Male or female 21-80 years of age
- Participated in the informed consent process and signed study specific informed consent document
- 3. Willing and able to comply with study procedures, including study visits and study dressing regimens
- 4. Confirmation of venous disease by non-invasive venous studies with either Doppler-confirmed venous reflux or having ≥ 2 clinical characteristics of venous insufficiency (varicose veins, lipodermatosclersosis, venous dermatitis, atrophie blanche, edema). Biopsy done to exclude other skin conditions e.g. cancer on ulcers ≥ 6 months
- 5. HbA1c of ≤ 10%
- 6. Have a venous ulcer between the knee and ankle, at or above the malleolus
- 7. Target wound size ≥4 cm² to ≤ 150 cm² in area without exposed tendon, muscle or bone
- 8. Target wound duration of at least 3 months and less than or equal to 12 months as of the date the subject signs consent for study
- 9. VLU may have characteristics that include yellow/white slough with or without fibrous/scar tissue and/or non-viable tissue, but not mandatory
- 10. Be willing and able (or have family member/friend willing and able) to apply required dressing changes as well as the ability of the subject to tolerate limb compression bandage

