#### Eligibility Criteria Diabetic Foot Ulcer (DFU):

#### **Inclusion Criteria:**

- 1. Male or female 21-80 years of age
- 2. Participated in the informed consent process and signed study specific informed consent document
- 3. Willing and able to comply with study procedures, including study visits and study dressing regimens
- 4. Diagnosed as having Type 1 or Type 2 diabetes
- 5. HbA1c of ≤ 10%
- 6. Presence of a DFU, Wagner 1 or 2 (see **Appendix 7** for definitions), extending at least through the dermis provided it is below the level of the medial or lateral malleolus. Any wound that has been present for ≥ 6 months and hasn't previously been biopsied, a biopsy must be performed to exclude other skin conditions e.g. cancer for ulcers. Also, if a clinical suspicion of malignancy exists in the opinion of the Investigator, a biopsy should be performed regardless of duration of wound
- 7. Target wound will be located on the foot or ankle and will be the largest ulcer if two or more DFUs are present with the same Wagner grade and will be the only one evaluated in the study. If other ulcerations are present on the same foot, they must be more than 1 cm distant from the target wound
- 8. Target wound (i.e. current episode of ulceration) has been present for greater than 4 weeks prior to screening visit and less than 12 months, as of the date the subject consents for study
- 9. Target wound size ≥0.25 cm² to ≤ 150 cm² post debridement at Screening Visit and Treatment Visit Week 1/Randomization

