# 10 Statistical Considerations (See Statistical Analysis Plan [SAP])

### 10.1 General Considerations and Populations

The primary endpoint is percent change from baseline in target wound measure by Week 12/End of Study.

All statistical testing will be performed at a two-sided alpha=0.05 level of significance. A detailed Statistical Analysis Plan (SAP) will be finalized prior to database lock.

All subjects who are randomized and receive at least one study treatment will be included in the Safety Population. All summaries of safety data will be based on this population and reported "as treated" – in case there are subjects that were not treated as per the randomization outcome.

All subjects who are randomized, receive at least one study treatment and have at least one post-baseline measure assessment will be included in the Intent-to-Treat Population (ITT). All efficacy summaries will be based on this population and will be reported according to the intent to treat principle (as randomized).

A review of major protocol violations will be performed. Major violations will include, but not be limited to, an assessment of compliance, use of concomitant medications and intercurrent illnesses. Subjects and data points without major protocol violations will be included as part of the Per-Protocol Population. If fewer than 10% of the subjects have major protocol violations, these analyses may not be performed.

All analyses and summaries will be reported overall and for each indication (venous leg ulcers and diabetic foot ulcers).

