## 10.2 Efficacy Analyses

Primary and Secondary Efficacy Analysis

1. The null hypothesis to be tested for the primary efficacy endpoint is: No differences between the TEST (Omeza® Products Bundle) and the Standard of Care.

The primary efficacy endpoint, percent change of wound measure from baseline at Week 4, Week 8 and by Week 12 will be analyzed using mixed model repeated measure (MMRM) with fixed effects factors of treatment and visit and subject as a random effect in the statistical model.

- 2. Time to maximum closure or complete closure can be defined as the time taken from the start of treatment till the closure (complete or maximum) of the ulcer. Time to closure data will be analyzed using Kaplan Meier Product Life Estimate with median, guartiles and 95% CI.
- 3. Wound reduction rate will be calculated at Week 4, 8 and by Week 12.
- 4. Proportion of subjects healed at Week 12 will be compared between TEST (Omeza® Products Bundle) and SOC.

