## 10.4 Sample Size Rationale

The power of the study is computed for the primary endpoint of "percent change from baseline in target wound measure by Week 12" comparing the two means. The combined sample size of 78 subjects (randomized 2:1) will provide over 80% power to detect a difference of about 14 units (percent change from baseline in wound measure by Week 12), assuming a standard deviation of 20 units, and a 2-sided significance level of 5%.

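### Primary MMRM omits baseline wound area and ulcer type, both known before randomization: a valid analysis that gives up some precision at no saving

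*Protocol*

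**What the plan says.** Section 10.2 names every term of the primary model for percent change in wound measure: "with fixed effects factors of treatment and visit and subject as a random effect in the statistical model". Neither baseline wound area nor indication is listed there. The Synopsis (Statistical Methods) names only the MMRM, and no other section adds a covariate.

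Both variables are available in time. Wound area is measured at Screening (Section 6.1) and again at the Week 1 baseline visit, where Section 6.2 lists it ahead of randomization and first treatment. Indication is known at entry because it decides which eligibility list in Section 4.2 applies.

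Eligible areas are wide. For DFU the criterion is "Target wound size ≥0.25 cm² to ≤ 150 cm² post debridement"; for VLU it is "Target wound size ≥4 cm² to ≤ 150 cm² in area". The two indications also differ in minimum ulcer duration (more than 4 weeks for DFU, 3 months for VLU) and in background care (offloading or compression).

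The powered comparison pools both indications. Section 10.4 states "The combined sample size of 78 subjects (randomized 2:1) will provide over 80% power"; its target is a 14-unit gap between arms at Week 12, with an SD of 20. The Synopsis plans 26 TEST and 13 SOC subjects in each indication. Section 4.3.2 describes blocked randomization with site-numbered codes and names no stratification by indication or wound size. Section 10.1 asks for results overall and for each indication.

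**The concern.** Dividing by baseline does not make percent change independent of starting size. A very small ulcer and a very large one need not have the same expected percent change over 12 weeks, and neither need a DFU and a VLU. If either variable predicts the outcome, leaving it out of the model has two effects. Its share of the variance stays in the residual and widens the interval for the treatment effect. In addition, any chance difference between arms on that variable carries over, in part, into the estimate. With only 26 SOC subjects such differences are not rare. At stake are the precision and credibility of the primary estimate, not the validity of the test.

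**Working it through.** **Inputs.** From Section 10.4: difference 14 units, SD 20, 78 subjects at 2:1 (52 TEST, 26 SOC). From Section 10.1: two-sided 5%. From the Synopsis: 26/13 per indication. Not in the protocol, so assumed over a range: the correlation rho of baseline log area with percent change, and the share R² of outcome variance that area and indication explain together.

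**1. The plan's own figure.**
- √(1/52 + 1/26) = 0.240, so the standard error is 20 × 0.240 = 4.80 and the noncentrality is 14/4.80 = 2.91.
- Power is 83.0% by normal approximation and 82.1% by noncentral t (76 df). The claim of over 80% reproduces without any covariate.

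**2. Span of eligible areas.** 150/0.25 = 600-fold for DFU and for the pooled trial; 150/4 = 37.5-fold for VLU. These are eligibility limits, not an expected distribution.

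**3. Power with both covariates.** Residual SD = 20 × √(1 − R²), with two further degrees of freedom spent (74 df).

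| R² (assumed) | Residual SD | Power |
|---|---|---|
| 0 | 20.00 | 82.0% |
| 0.05 | 19.49 | 83.9% |
| 0.1 | 18.97 | 85.8% |
| 0.2 | 17.89 | 89.5% |

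If the covariates explain nothing, the loss is 82.1 − 82.0 = 0.1 point. This treats Week 12 as a single outcome. The protocol gives no between-visit correlations from which the repeated-measures figure could be derived.

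**4. Chance imbalance in baseline area.**
- The arm difference in mean baseline log area has a standard error of 0.240 SD, so P(|difference| > 0.3 SD) = 2 × [1 − Φ(0.3/0.240)] ≈ 21%.
- An imbalance of 0.3 SD shifts the unadjusted estimate by 0.3 × rho × 20 units: 1.2 at rho = 0.2, 1.8 at rho = 0.3, 3.0 at rho = 0.5. The target difference is 14.
- Within one indication (26/13) the standard error is √(1/26 + 1/13) = 0.34 SD.

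**5. Indication.** If 26/13 is met in each indication, both arms are half VLU and half DFU, so no imbalance in ulcer type carries over. Omitting the term still costs precision, because the model's standard error counts between-type variation that the split has already removed from the estimate. A simulation (4,000 runs per scenario, single Week 12 outcome, overall SD 20, split enforced) shows the size:
- Types 20 units apart: power 85% unadjusted and 91% adjusted; unadjusted type I error 2.4%. Under the null the average model standard error is 4.80, while the estimate's actual SD is 4.20.
- Types 10 units apart: power 83% unadjusted and 85% adjusted (83.2% and 84.5%); type I error 4.9%, so the conservatism is negligible.

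The protocol gives no difference between types, so both are illustrations.

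**The case against.** The strongest reply is that nothing in the plan is broken. Under randomization the unadjusted estimate is unbiased on average, type I error was 2.4% to 5.6% across the simulated scenarios, and the stated power is reached without covariates. That stands. The outcome is already scaled by baseline, so the remaining correlation with area may be small; no correlation is given. That also stands, and is why the gain can only be shown as a range.

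A reader might go further than the documents allow in four ways:
- **That pooling without an indication term drops power to 73–80%.** Those values (79.7%, 76.9% and 73.0% for types 10, 15 and 20 units apart) require SD 20 to hold within each indication and ignore the planned 26/13 split. Section 10.4 attaches the SD to the combined sample without saying which SD it is. With an overall SD of 20 and the split met, simulated unadjusted power is 82.6%, 84.0% and 85.3%.
- **That the gain is about 9 points.** This is rho = 0.5 (91.3% against 82.1%), which nothing in the protocol supports. For area alone, rho = 0.2 gives 83.6% and rho = 0.3 gives 85.4%.
- **That imbalance passes undiminished into the estimate.** It is attenuated by rho, and for ulcer type it vanishes if the split is met. Section 4.3.2 names no mechanism that guarantees the split, so that protection is planned but not secured.
- **That the comparison of proportions healed has the same flaw.** Section 10.2 names no method for it, so there is no stated choice to criticise.

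Finally, a SAP is promised, and baseline area, being continuous, might not appear in a list of factors. This softens the point for area, less so for indication, which is a factor. Since the protocol spells out the model terms, a change there is still in order.

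**Conclusion.** The point holds as an improvement at almost no cost, not as the correction of an error. The primary model leaves out two variables known before randomization. The analysis remains valid and reaches 82.1% power on its own inputs. The loss is precision, plus whatever chance imbalance in baseline area the trial happens to draw: about a 21% chance of more than 0.3 SD, worth about 1.8 units at rho = 0.3. Adjustment would raise power from 82.1% to between 83.9% and 89.5% for R² between 0.05 and 0.2, and costs about 0.1 point if the covariates explain nothing. For ulcer type, if 26/13 per indication is met, omission costs only precision and makes the test conservative, to a degree that depends on how far apart the types are. All sizes rest on assumed R² or rho and on a single-timepoint approximation.

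**What to change.** In Section 10.2 and the Synopsis (Statistical Methods), add two fixed covariates to the primary MMRM: log-transformed target wound area measured at Week 1 before randomization, and indication (VLU/DFU). The log scale keeps a few very large ulcers from dominating a covariate that may span 600-fold. Drop indication from the per-indication models. Keep the present unadjusted model as a sensitivity analysis.

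The cost is two degrees of freedom and a change of wording, with no new data. Because the trial is open label, the covariates should be fixed before outcome data are examined, so that their choice cannot be questioned later.

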#### Statistical Methods

Efficacy analyses will be conducted under the intent to treat principle. Analyses will be performed on each of the two indications (venous leg ulcers and diabetic foot ulcers) and overall. Analyses to include the primary endpoint of:

- % change from baseline (Treatment Visit Week 1) in ulcer measure at Treatment Visit Week 4,
   Week 8 and by Week 12/End of Study using a mixed model repeated measure (MMRM)
- Ulcer size closure rate will be reported at Treatment Visit Week 4, Week 8 and by Week 12/End of Study.
- Time to maximum closure or complete closure will be assessed using Kaplan-Meier estimation, with medians, quartiles, and 95% confidence intervals (CIs).
- Incidence of DFU and VLU will be analyzed by comparing the proportion of subjects healing at week 12/End of Study.

Further analysis may also be conducted using age category as a subgroup.

Descriptive statistics will be provided for subject demographics, safety, and exposure data and will include the number of observations, mean, standard deviation (SD), median, and range for continuous variables and number and percent for categorical variables; 95% CIs will be presented where appropriate.

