### 3 Study Design

### 3.1 Description of the Study Design

This is a randomized, multicenter, open-label study comparing the Omeza® Products Bundle versus standard of care treatments for 2 different types of chronic ulcers (venous leg ulcers and diabetic foot ulcers). The treatment period will be 12 weeks, with subjects coming into the study site weekly for evaluations, photography and formal measurements of the target wound, and dressing changes. There will be a total of 13 study site visits. The Screening Visit (Day 0) will occur 1 week prior to randomization and will include routine labs and vascular assessment to determine inclusion/exclusion of the potential subject from the study; followed by weekly treatment visits (Week 1 through Week 11); randomization will occur at Treatment Visit Week 1; the Treatment Visit Week 12/End of Study Visit will include end of study labs. Target wounds will be photographed and measured, and vascular assessment will be done at each of the 13 visits. Standard of care will be billed to subject's insurance for both TEST and SOC.

If the wound closes before Week 12, the subject will continue to come in for all the remaining study visits until study completion. If the wound does not close by Week 12, the subject will be immediately exited from the study and no further follow-up will occur as part of the study.

Table 1: Study Plan

Study Period	Visit	Purpose
Screening	Screening (Day 0)	Determine eligibility, routine labs,
		vascular assessment, photos and
		measures
Baseline /	Treatment Visit Week 1	Review eligibility, randomization,
Randomization		Wound-QoL questionnaire, vascular
		assessment, photos and measures,
		begin study treatments.
Treatment	Treatment Visits Week 2 - Week	Study treatments, vascular assessment,
	11	photos and measures
End of Study Visit	Treatment Visit Week 12	End of Study routine labs, vascular
		assessment, photos and measures,
		Wound-QoL questionnaire

For subject to be eligible they must meet entry criteria. If the subject is not found eligible at Treatment Visit Week 1, the subject may be re-screened once or may be replaced.

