### 3.2 Study Endpoints

#### Primary Endpoint:

- 1. Percent Change from Baseline in target wound measure at Week 4, Week 8 and by Week 12.
- 2. Ulcer Size Closure rate at Week 4, Week 8 and by Week 12.
- 3. Time to maximum closure or complete closure.
- 4. Incidence of DFU and VLU healing at Week 12.

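### The time endpoint counts maximum as well as complete closure as its event, so an early stall scores like fast healing and the Kaplan-Meier median has no clear direction

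*Protocol*

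**What the plan says.** Section 3.2 of the protocol lists "Time to maximum closure or complete closure" as item 3 under its primary endpoint heading. The synopsis repeats the endpoint among the efficacy criteria and under Statistical Methods.

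Section 10.2, item 2, gives the definition: "Time to maximum closure or complete closure can be defined as the time taken from the start of treatment till the closure", with the closure then qualified as ("complete or maximum) of the ulcer". The analysis is by estimation: "Time to closure data will be analyzed using Kaplan Meier Product Life Estimate with median", quartiles and 95% confidence intervals. The protocol states no minimum reduction for a maximum closure, no censoring rule and no between-arm test for this endpoint.

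Two other provisions bear on it. Under section 10.1, efficacy summaries use subjects who were randomized, were treated and "have at least one post-baseline measure assessment will be included in the Intent-to-Treat Population (ITT"). Under section 3.1, wounds are measured weekly, and "If the wound does not close by Week 12, the subject will be immediately exited from the study".

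**The concern.** Complete closure is a success that some subjects never reach. Maximum closure is simply the point at which a wound was smallest, and every measured wound has one. Joining the two with *or* mixes successes with failures, and a shorter time is read as better for both.

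A wound that shrinks by 10% at the first weekly visit after baseline and then worsens scores 1 week. A wound that closes fully at 9 weeks scores 9. A subject who leaves early has a smallest area at or before the last visit and, on the literal definition, an early event. The maximum is also known only once follow-up has ended.

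At stake is whether the reported medians and curves can be read at all. If they cannot, an open-label trial would publish a time-to-closure figure, under a primary heading, that may favour the arm in which fewer wounds closed.

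**Working it through.** **The plan's own figure.** The only stated figure is the power for percent change: 78 subjects at 2:1 (52 and 26), difference 14, SD 20, two-sided 5%. The standard error is 20 × √(1/26 + 1/52) = 4.80, and 14/4.80 = 2.91. Normal-approximation power is Φ(2.91 − 1.96) = 83.0%, and the noncentral t gives 82.1%. Both agree with the claim of over 80%. No figure is given for the time endpoint.

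**Consequence of the definition.** The analysis set requires a post-baseline measurement, so each analysed subject has a smallest observed area. If that is the event, there is no censoring, and the Kaplan-Meier estimate is the empirical distribution of the visit of smallest area.

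**Illustration 1, by hand (all inputs assumed).** Closures fall evenly over weeks 5 to 11, early stalls over weeks 1 to 5, and continued shrinkage without closure ends at weeks 9 to 11. Arm A closes 50% of wounds and arm B 30%. The median is the first week at which cumulative events reach 50%.

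*Unequal stall shares: 30% of A's non-healers and 70% of B's stall early.*
- A: stalls 0.30 × 50 = 15%, continued shrinkage 35%. Week 8: 15 + 50 × 4/7 = 43.6%. Week 9: 15 + 50 × 5/7 + 35/3 = 62.4%. Median 9.
- B: stalls 0.70 × 70 = 49%, continued shrinkage 21%. Week 4: 49 × 4/5 = 39.2%. Week 5: 49 + 30/7 = 53.3%. Median 5.

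*Equal stall shares in both arms.*
- 30%: A is as above, median 9. B has 21% stalls and 49% continuing: 21 + 30 × 4/7 = 38.1% at week 8; 21 + 30 × 5/7 + 49/3 = 58.8% at week 9. Median 9.
- 50%: A is 25 + 50 × 3/7 = 46.4% at week 7 and 25 + 50 × 4/7 = 53.6% at week 8. B is 35 + 30 × 3/7 = 47.9% and 35 + 30 × 4/7 = 52.1%. Medians 8 and 8.
- 70%: A is 35 + 50 × 2/7 = 49.3% at week 6 and 35 + 50 × 3/7 = 56.4% at week 7, median 7. B has median 5, as above.

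**Illustration 2, simulation (all inputs assumed).** There are 100,000 subjects per arm with weekly areas at 1 to 11 weeks after baseline. Healers close at a mean of about 8 weeks (SD 2). Non-healers stall with 50–90% of baseline area left and then enlarge slightly. Stall timing is the same in both arms. Each cell gives the better arm against the worse: median weeks as the endpoint is written, with means in brackets.

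| Healing | Stall 2–5 wk | Stall 4–8 wk | Stall 7–11 wk |
|---|---|---|---|
| 40% v 20% | 5 v 4 (5.28 v 4.40) | 7 v 6 (6.78 v 6.39) | 9 v 9 (8.59 v 8.79) |
| 50% v 30% | 5 v 4 (5.72 v 4.84) | 7 v 7 (6.98 v 6.59) | 9 v 9 (8.47 v 8.69) |
| 60% v 20% | 6 v 4 (6.16 v 4.40) | 7 v 6 (7.17 v 6.38) | 8 v 9 (8.37 v 8.79) |
| 60% v 40% | 6 v 5 (6.16 v 5.29) | 7 v 7 (7.17 v 6.78) | 8 v 9 (8.37 v 8.58) |
| 70% v 30% | 7 v 4 (6.62 v 4.82) | 7 v 7 (7.36 v 6.58) | 8 v 9 (8.28 v 8.67) |

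Early stalls reverse every pair. Stalls at 4–8 weeks reverse the means but often tie the medians. Late stalls put the means in the right order, with medians right or tied. For 60% against 20% with stalls at 2–5 weeks, 5% measurement noise gives medians of 7 v 5 and 10% gives 7 v 6, still reversed.

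**With complete closure as the event and the rest censored.** For 60% against 20%, events fall from 100% in both arms to 60% and 20%, and the medians are 10 weeks against not reached. The order is correct.

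**The case against.** The strongest reply concerns status. Section 10.1 names percent change by Week 12 as the primary endpoint, section 10.2 attaches the null hypothesis and the mixed model to it, and section 10.4 powers it alone. Time to closure gets estimates only, and the proportion healed at Week 12 is compared separately, so an arm with fewer closures would show there. This stands. A reader might infer from section 3.2 that a confirmatory conclusion is at risk; the later sections do not support that. It does not rescue the time endpoint, which still sits in a primary list.

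A second reply is that the size is built into the assumptions. This also stands. The 9 against 5 weeks gives the worse arm more than twice the early-stall share; equal shares of 30% or 50% tie. A reader might infer that the worse arm will look faster, but the documents give no closure or stall rates from which to say so.

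A third is that censoring is a matter for the statistical analysis plan. In part it is. The protocol does not state that nobody is censored or that a dropout counts as an event; both follow only from reading the definition literally. But the protocol itself fixes the event as complete or maximum, and a later censoring rule would not remove the word maximum.

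The exclusion of some randomized subjects from the analysis set is a separate question, and this point does not depend on it.

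**Conclusion.** The definition is wrong as written and should be corrected before analysis. Read literally, it gives every analysed subject an event and makes the median ambiguous in direction. Across the assumed scenarios the arm medians reverse (by up to 4 weeks, 9 against 5), tie, or keep the right order. The result turns on whether non-healing wounds stall before or after the usual closure time, and on whether stall shares differ between arms. All these inputs are assumptions.

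The ambiguity itself needs no assumption beyond the literal reading. Its consequence is a misleading estimate and curve on a listed endpoint. The percent-change test, its stated power and the comparison of proportions healed are unaffected.

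**What to change.** Redefine the endpoint in section 3.2 (item 3), section 10.2 (item 2) and both synopsis entries as time from first study treatment to first complete closure of the target wound. Censor subjects whose wounds have not closed at their last wound measurement. Report Kaplan-Meier curves with medians, quartiles and 95% confidence intervals, overall and by indication. Report maximum percent reduction separately, as a descriptive measure of size.

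A between-arm log-rank test is not needed to cure the defect. If one is added, it should be optional and labelled secondary.

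The cost is wording only, since weekly wound measurements are already collected. The downside is that a median may not be reached where fewer than half the wounds close. In the simulation this happened in every arm with healing of 40% or less.
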